All participants will undergo standard admission and pre-operative procedure for primary total knee arthroplasty per institution protocol. Participants will be admitted to hospital on day of surgery for elective procedure. Spinal anaesthesia will be placed in pre-op holding area per regional anaesthesia team. Participants will be positioned in standard supine position. Per operative protocol each patient will undergo standard prep and drape. There will be no application of tourniquet for those randomized to no-tourniquet arm. If tourniquet is to be used, it will be applied after induction and will be deflated after incision closure. Maximum tourniquet time will be 120 mintues, TKA implant choice will be made based on surgeon preference. Transexamic acid will be given 1g IV prior to incision and 1g IV at end of case. The procedure for all participants will be via midvastus approach to the knee. At the end of the procedure, all patients will receive standard ipericapsular injection of 30mL 0.25% Marcaine with epinephrine and 30mL toradol prior to closure.

PT treatment and evaluation will take place on day of surgery post-operative day one prior to discharge. All patients will be placed on Aspirin EC 325mg BID for VTE prophylaxis. Pain medications will be standardized during admission, and an uncontrolled pain protocol will be available for implementation at physician discretion; see Tables 1 and 2) The final set of standard blood labs will be drawn at midnight. Discharge medications will be standard(Table 3)., Patients will be contacted at 1 week post-operatively to evaluate clinical progress, general concerns and compliance with study protocols, including use of the Fitbit HR platform and FocusMotion platforms.

Participants will be scheduled for a standard clinical visit at 4 weeks.

Participants will undergo final clinical evaluation at 3 months post-operatively with a PT visit and phone call from the research team as well as a final questionnaire about their experience with the app and Fitbit and knee brace which will be completed by paper, phone, or electronically.

Fitbit Activity Tracker and Focus Motion knee brace apps

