Balance: tandem stance	scale	PT measurement
Balance: Standing on One Leg	scale	PT measurement
10m walk test for speed	seconds	PT measurement
6 minute walk test	meters	PT measurement
Timed up and go test	seconds	PT measurement
5 times sit to stand	seconds	PT measurement
30 sec chair stand	count	PT measurement
Timed stair climb	seconds	PT measurement
Quadriceps strength	N	PT measurement
Hamstrings strength	N	PT measurement
PSQI	scale	FocusMotion App Survey
Oxford Knee Score	scale	FocusMotion App Survey
% normal knee	scale	FocusMotion App Survey
FJS	scale	FocusMotion App Survey
VAS pain score	scale	FocusMotion App Survey
Use of assistive device	incidence	FocusMotion App Survey

Narcotic requirement	daily MME/hr	FocusMotion App Survey
Sleep duration	min	Fitbit
Sleep disturbances	count	Fitbit
Sleep efficiency (time asleep/time in bed)	percentage	Fitbit
Sleep quality (REM sleep/non-REM sleep)	percentage	Fitbit
PROMIS	score	WUPRO
Wound complications	incidence	EPIC documentation
DVT/PE	incidence	incidence
Infection	incidence	EPIC documentation
Return to OR	incidence	EPIC documentation
Patient questionnaire about app and Fitbit/brace usage	questionnaire	Paper questionnaire or through app

REFERENCES

Dennis, D. A. ;Kittelson, A. J. ;Yang, C. C. ;Miner, T. M. ;Kim, R. H. ;Stevens-Lapsley, J. E. Does Tourniquet Use in TKA Affect Recovery of Lower Extremity Strength and Function? A Randomized Trial. 2016. Clin Orthop Relat Res; 474(1): 69-77

Huang, Z. Y. ;Pei, F. X. ;Ma, J. ;Yang, J. ;Zhou, Z. K. ;Kang, P. D. ;Shen, B. Comparison of three different tourniquet application strategies for minimally invasive total knee arthroplasty: a prospective non-randomized clinical trial. 2014. Arch Orthop Trauma Surg; 134(4): 561-70.

Kageyama, K. ;Nakajima, Y. ;Shibasaki, M. ;Hashimoto, S. ;Mizobe, T. Increased platelet, leukocyte, and endothelial cell activity are associated with increased coagulability in patients after total knee arthroplasty. 2007.

J Thromb Haemost; 5(4); 738-45

Liu, D. ;Graham, D. ;Gillies, K. ;Gillies, R. M. Effects of tourniquet use on quadriceps function and pain in total knee arthroplasty. 2014. Knee Surg Relat Res; 26(4); 207-13.

Nishiguchi, M. ;Takamura, N. ;Abe, Y. ;Kono, M. ;Shindo, H. ;Aoyagi, K. Pilot study on the use of tourniquet: a risk factor for pulmonary thromboembolism after total knee arthroplasty? 2005. Thromb Res; 115(4); 271-6.

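### Seven of the 3-month patient-reported items (all except PROMIS) have the FocusMotion app survey as their only listed source; no paper or phone fallback is stated, although one is written for the device-experience questionnaire.

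*Combined protocol and SAP*

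**What the plan says.** METHODS, Data collection, says that the tables list all the data to be collected, so the source column of Table 7 defines how each 3-month item is obtained.

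- **Contacts at 3 months.** Participants have a "final clinical evaluation at 3 months post-operatively with a PT visit and phone call from the research team". No outcome survey is assigned to either contact.
- **Device-experience questionnaire.** The text describes "a final questionnaire about their experience with the app and Fitbit and knee brace which will be completed by paper, phone, or electronically". The matching Table 7 row reads "Paper questionnaire or through app".
- **Patient-reported outcomes.** The rows read, for example, "PSQI scale FocusMotion App Survey", "Oxford Knee Score scale FocusMotion App Survey" and "FJS scale FocusMotion App Survey". The rows for % normal knee, VAS pain, assistive-device use and narcotic requirement name the same single source.
- **PROMIS.** Its listed source is WUPRO. The document does not describe how WUPRO is administered.

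**The concern.** The plan accepts paper and phone answers for opinions about the technology but states no such route for the outcomes that the technology is meant to measure. Staff could be in the same room as a patient, or on the phone, and have no written instruction to obtain an Oxford Knee Score or a PSQI.

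Stopping the app is unlikely to be unrelated to outcome: pain, fatigue and slow recovery could each contribute, as could low confidence with phones. The 3-month values that remain would then describe people who kept using the app. If tourniquet use affects pain, persistence with the app could also differ by arm, but the documents give no means of sizing or signing that effect. The affected items matter: VAS pain is the measure used for the sample size, PSQI is the named subjective instrument of Specific Aim 3, and patient-reported surveys are part of Specific Aim 2.

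**Working it through.** **1. Sources in Table 7, counted by row.**

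| Source | Rows | Left if the app is stopped but the visit attended |
|---|---|---|
| FocusMotion app survey | 7 (PSQI, Oxford Knee Score, % normal knee, FJS, VAS pain, assistive device, narcotic requirement) | No stated route |
| PT measurement | 12 | Yes |
| Fitbit | 4 sleep rows | Yes, if the Fitbit is still worn |
| FocusMotion brace | 1 (active ROM) | Depends on the brace, not the survey |
| WUPRO | 1 (PROMIS) | Separate source |

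**2. Does any other section supply a fallback?**
- *Data collection:* the content of the 3-month call is not specified.
- *Data Security:* paper copies of questionnaires are to be filed, but no instrument is named. The device questionnaire alone could account for that sentence.
- *Participants Lost to follow-up:* the steps aim to bring people back to clinic or establish their status. They offer no other survey mode for someone who attends without using the app.
- *Compliance:* the one stated check on platform use is at 1 week, while use is expected for 3 months.

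None of these states a fallback.

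**3. The plan's own sample size.** Inputs from Number of participants: d = 0.5, power 0.80, alpha 0.05 (taken as two-sided), 10% dropout. Equal arms are assumed.
- Normal approximation: n per arm = 2(1.960 + 0.842)²/0.5² = 62.8, so 63.
- Exact t-test: 63.77, so 64 per arm and 128 in total, as stated.
- Dropout: 64/0.9 = 71.1, so 72 per arm and 144 in total, as stated.

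The calculation reproduces. It has one 10% allowance and nothing separate for app non-use.

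**4. Illustrative size.** The share who stop the app but still attend is an assumption: 144 × 0.10 = 14.4, about 14 patients; 144 × 0.30 = 43.2, about 43 patients.

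**5. What that would do to a 3-month VAS comparison.** If 10% are lost altogether and a further 10% to 30% attend without app data, total missingness is 20% to 40%. Two-sided t-test power at d = 0.5, with n = 72 × (1 − share missing) per arm:

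| Missing, all causes (assumed) | Evaluable | Power |
|---|---|---|
| 10% | 130 | 0.81 |
| 20% | 115 | 0.76 |
| 30% | 101 | 0.70 |
| 40% | 86 | 0.63 |

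The plan does not fix the time point of the primary VAS analysis, so these figures show scale only. They cover lost precision, not bias.

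**The case against.** Several stronger readings are tempting, and the documents do not support them.

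- *All 3-month patient-reported data are lost.* PROMIS has a different source.
- *Stopping the app amounts to withdrawal from Aims 1 to 3.* No section says so. Aim 2 keeps 12 physiotherapy measures and Aim 3 keeps Fitbit sleep data. Aim 1 rests on daily assessment, so entries made before stopping remain, as do the nursing VAS scores and chart-reviewed narcotic use in Table 5. The background section stresses the early postoperative period.
- *Stopping the brace stops the surveys.* In Table 7 the brace supplies active ROM only, and nothing makes the survey depend on wearing it.
- *The plan forbids another route.* It is silent. The call could be used to prompt or collect answers, and paper questionnaires are foreseen in general terms.

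The plan also has features that support app use: a capable smartphone is required at entry, devices are used for 2 weeks before surgery, compliance is checked at 1 week, and $100 follows the 3-month evaluation. The 10% to 30% range is only an assumption, and no analysis method is specified that would show how missing values are to be treated. Finally, a visual analogue scale cannot be marked by telephone, so a phone route does not suit every item.

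All of this stands, and it limits the point. It does not fill the gap: the supportive features encourage app use but give no instruction for the patient who has stopped and is nonetheless in contact.

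**Conclusion.** The point holds as an omission in data collection. Seven 3-month self-reported items have one listed source and no stated fallback, while a paper or phone route is written only for the device-experience questionnaire. The resulting missing data would be avoidable and plausibly related to outcome.

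The size is unknown. The illustration of 14 to 43 patients rests wholly on the assumed 10% to 30%, and the power figures rest on that assumption plus a 3-month VAS comparison that the plan does not name as primary. The conclusion also assumes that the seven printed tables are complete on this point, although the text counts to Table 8. It does not challenge the sample size, which reproduces. It is a cheap improvement worth making before patients reach 3 months, because a missed 3-month response cannot be recovered later.

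**What to change.** In the 3-month paragraph of Data collection and in the Table 7 source column, state that when no 3-month app entry exists:

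1. the seven items are completed on paper at the PT visit, or by phone at the research call for those that can be asked verbally;
2. VAS pain is kept on paper, or a spoken rating is recorded as a separately flagged numeric score and not entered as a VAS value;
3. the mode of completion is recorded for every item.

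Add one sentence saying that stopping the app is not withdrawal from the study, so visits, calls and chart review continue unless consent is withdrawn.

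The cost is paper and phone copies of existing instruments, used at contacts already planned. The downside is mixed mode of administration in a minority, which a sensitivity analysis using the mode flag can check. The change recovers the 3-month values only; daily app entries missed before then stay missing.

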Title:

Impact of Tourniquet Use on Functional Outcomes and Complications after TKA

Principal Investigator:

[name]

Co-Investigators:

[name]

[name]

[name], PT, DPT, MSCI

[name]

OVERVIEW

Background information:

Functional recovery after total knee arthroplasty (TKA) has seen dramatic improvement over the past 20 years through advances in surgical technique, implant design, perioperative pain management strategies, and physical therapy protocols. Tourniquet use during TKA, however, remains controversial due to conflicting reports in the literature on these benefits and risks of its use. Reported advantages of tourniquet use include improved visualization of the surgical field and decreased intraoperative blood loss. (Austin, 2019) Reported disadvantages of tourniquet use include increased postoperative pain and slower functional recovery as a direct result of the pressure of the tourniquet on the thigh during the procedure. (Ejaz 2014, Harsten 2015)

Traditionally with tourniquet use during TKA, the limb is exsanguinated and the tourniquet is raised to a fixed, pressure at the beginning of the case, typically 250mmHg to 350mmHg, and let down after closure. A novel tourniquet design that adjusts the tourniquet pressure in real-time based on intraoperative patient blood pressure measurements. This design may allow for the tourniquet to be inflated at a lower mean pressure while still maintaining efficacy.

A prospective study comparing total blood loss, pain and functional recovery after TKA using this novel tourniquet design, design (Zimmer A.T.S.® 4000TS Automatic Tourniquet System, with disposable contour cuffs) and TKA without tourniquet would further the current literature. Total blood loss will be calculated by previously validated methods. Pain and functional recovery will be closely monitored throughout the postoperative period using a patient wearable activity tracker (FitBit Inspire HR) and a smartphone-based patient engagement platform with integrated digital

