During the pre-operative arthroplasty class, participants in the study will be set-up with a FitBit wrist-based activity tracker and FocusMotion knee brace and the appropriate software. Participants will be instructed to use the device in the 2 weeks prior to undergoing surgery, to gather baseline data on narcotic use, pain, use of assistive device and sleep quality. They will continue to use the devices for 3 months postoperatively(Table 7).

Subject Payment

Honorarium of \$100 provided at 3 months following completion of 3 month evaluation. Participants will be gifted the Fitbit Inspire HR and the FocusMotion smart-brace and platform and given an honorarium of \$50 for completion of the 1 year app based survey.

Participants Lost to follow-up: Some participants will not return for follow-up at the required intervals. A member of the research team shall contact non-respondent participants using phone calls, regular mail, e-mail, certified letters, or other means to urge participants to return for clinic follow-up or ascertain if a participant has moved, died, or otherwise become lost to follow-up. The following flow chart identifies the steps for attempts to locate lost participants. These actions, along with any other options available to the site, should be followed to exhaust all reasonable means in locating lost participants. These actions should be documented in the participant's records and may be performed concurrently or in parallel.

Phone call to last known number → Contact → Follow-up with participant

↓

No Contact

↓

Phone call to other numbers (spouse, relative, etc.) → Contact → Follow-up with participant

↓

No Contact

Note: There will be a minimum of 3 calls to different numbers

↓

Mail letter to last known patient address → Contact → Follow-up with participant

↓

No Contact

↓

Mail letter to secondary addresses → Contact → Follow-up with participant
↓
No Contact
↓
Mail “certified” type of letter to last address and any secondary address → Contact → Follow-up with participant
↓
No Contact
↓
Social Security Death Index to determine if participant has died → Confirm death
↓
Not Confirmed
↓
End attempts.

INFORMED CONSENT

Enrollment and consent will begin in the clinics of [name], [name] and [name], and will be the same for both study groups. The consent process will occur by one of the following means:

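### Post-discharge complications rest on EPIC alone, with no commitment to ask patients about outside care and no rule for unknown status, so events are liable to be missed

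*Combined protocol and SAP*

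**What the plan says.** The title makes complications a subject of the trial: "Impact of Tourniquet Use on Functional Outcomes and Complications after TKA". The stated purpose and Specific Aims 1 to 4 cover pain, functional recovery, sleep and blood loss, and do not name complications.

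Table 7 (3 months) lists four complication rows. Three name a source, and in each it is "EPIC documentation" alone: "Wound complications incidence EPIC documentation", "Infection incidence EPIC documentation" and "Return to OR incidence EPIC documentation". In the DVT/PE row, the unit is repeated in the column that should say who collects the item. Before discharge, Table 5 takes transfusion and perioperative complications from chart review.

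The Methods section, under Data collection, describes three contacts after discharge:

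- **1 week:** "Patients will be contacted at 1 week post-operatively to evaluate clinical progress, general concerns and compliance with study protocols", including use of the devices.
- **4 weeks:** a standard clinic visit.
- **3 months:** a final evaluation with a "PT visit and phone call from the research team", plus a questionnaire about the app, tracker and brace.

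The section on participants lost to follow-up accepts that "Some participants will not return for follow-up at the required intervals" and sets out tracing by telephone, letter, certified letter and a death index. It does not say how the complication status of a patient who is not found enters the analysis.

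**The concern.** A chart records what reaches it. A patient treated for a clot or a wound problem at another hospital enters these data only if the event is visible in EPIC or somebody learns of it and charts it. The protocol speaks to every patient who can be reached on three occasions, yet it does not commit to asking about complications on any of them, and it describes no request for outside records. The gap is widest after the 4-week clinic visit, because no further surgeon visit is described before the 3-month evaluation.

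Patients who stop attending raise a related problem. When an incidence is read from a chart and no rule says otherwise, no entry tends to become no event.

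At stake are the absolute complication rates in both arms, which would be too low. The comparison between arms would also suffer if capture or dropout differed. A report that complications did not differ would then rest partly on incomplete recording.

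**Working it through.** **Inputs from the protocol.** 128 evaluable patients, 10% dropout, 144 enrolled, two arms (taken here as equal).

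**The plan's own figure.** A two-sided two-sample t-test with effect size 0.5, alpha 0.05 and power 0.80 needs 63.77, so 64 per arm and 128 in total. With dropout, 64/0.9 = 71.1, so 72 per arm and 144 in total. Both figures reproduce. They concern VAS pain; the protocol gives no complication rate, event count or power.

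**Assumptions, not in the protocol.** True complication rates as shown below; 10-30% of events missed by the chart (capture 70-90%); and, where stated, lost patients scored as event-free for the whole period. The last is a worst case, since events before loss could be charted.

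**Events missed per arm.** At a true rate of 5%, expected events are 0.05 × 72 = 3.6. Missing 10% loses 0.36 and missing 30% loses 1.08, so about 0.4 to 1.1 events per arm.

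**What zero observed events would mean.** The one-sided 95% upper limit is 1 − 0.05^(1/n).

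- n = 72: 4.1%.
- Corrected for capture: 4.07/0.9 = 4.5% and 4.07/0.7 = 5.8%.
- 10% lost is about 7 per arm. Treating them as unknown leaves n = 65 and a limit of 4.5%, before any loss of capture.

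**Effect on a comparison.** Observed rate = true rate × (1 − lost) × (1 − missed). With assumed true rates of 10% and 5%, and 72 per arm:

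| Lost | Missed | Observed rates | Risk difference (points) | Expected events, both arms | Power |
|---|---|---|---|---|---|
| 0 | 0 | 10.0% v 5.0% | 5.0 | 10.8 | 0.21 |
| 10% | 0 | 9.0% v 4.5% | 4.5 | 9.7 | 0.19 |
| 10% | 30% | 6.3% v 3.15% | 3.15 | 6.8 | 0.14 |

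The risk ratio is 2.0 in every row, because equal under-capture cancels.

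**Unequal capture.** If true rates are equal but 10% of events are missed in one arm and 30% in the other, the apparent risk ratio is 0.9/0.7 = 1.29.

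**The case against.** The strongest case on the other side is that much of the harm is inferred. A reader might conclude that the plan counts lost patients and outside events as event-free. No passage says so. The plan is silent: it does not call them event-free, missing or censored. The defect is an absent rule, with event-free as the likely default of chart-only extraction.

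Three further inferences go beyond the text:

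- **That outside events have no route into the data.** A patient can mention one at the 1-week contact, the clinic visit or the 3-month evaluation, and it can then be charted. What is missing is a commitment to ask.
- **That a patient who drops out has an empty chart.** The surgical stay and any earlier visits are charted, and the tracing steps are documented in the participant's records.
- **That EPIC holds only this institution's care.** The documents do not say whether outside records appear in it. If they do, the gap is smaller.

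The DVT/PE cell is probably a typing slip, and a fault in reading the PDF cannot be excluded. Alone, it would be a clerical correction.

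Materiality is also limited. No complication hypothesis is planned. Even with perfect capture, power for 10% v 5% is about 0.21. Missing 0.4 to 1.1 events per arm compares with a binomial standard deviation of √(72 × 0.05 × 0.95) = 1.85. Nothing in the documents shows that loss would differ by arm, and patients are blinded.

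All of this stands and limits the point to likely under-recording. It does not remove it: the title promises complications, Table 7 counts them, and events never asked about are hard to recover after follow-up ends.

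**Conclusion.** The concern holds in a limited form. Followed as written, the plan would probably under-record post-discharge complications, because three rows rely on EPIC alone, the DVT/PE row has no readable source, no contact is committed to asking, and unknown status has no rule.

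The expected shortfall is about one event per arm or less, under the assumed 5% rate and 70-90% capture. Equal under-capture lowers the rates, the risk difference and the power but leaves the risk ratio unchanged; bias in the ratio needs unequal capture or loss. The primary pain outcome and the sample size are unaffected. This is an inexpensive improvement that should be made, not a threat to the trial's main conclusion.

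**What to change.** 1. At the 1-week contact, the 4-week visit and the 3-month call, ask a short fixed set of questions: any emergency visit, admission, clot, wound problem, infection, bleeding or transfusion, or re-operation, at any hospital, with date and place. Request the outside record when the answer is yes.
2. In Table 7, give patient report plus EPIC as the source for every complication row, including DVT/PE.
3. State the denominator rule: a patient without a 3-month contact is unknown after last contact, not event-free.
4. Optionally, add rows for readmission, later transfusion or bleeding, and death. The tracing steps already look deaths up, but Table 7 has no row for them.

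The cost is one CRF page and occasional record requests, with no new visit or staff and no change to the sample size. The downside is that more minor events will be reported, so the stated complication rates may be slightly higher.
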